A pilot randomized controlled trial of low molecular weight heparin or no treatment following cesarean
delivery

NCT06118957
09.03.2024

BACKGROUND

Venous thromboembolism (VTE) contributes to 9% of maternal deaths but we are lacking in evidence-based preventative interventions. Maternal mortality rates in the U.S. exceed those of other developed countries, and excessive national rates have demanded attention from both the academic community and lay public. As a leading contributor, VTE is a prime target for practice changes. The postpartum epoch is the highest risk period for VTE, and national guidelines have called for institutional protocols to categorize risk in postpartum individuals and implement corresponding pharmacologic thromboprophylaxis in an effort to reduce the incidence of postpartum VTE.

Pharmacologic prophylaxis with low molecular weight heparin (LMWH) is effective in reducing VTE peri-operatively in non-obstetric surgical fields. Guidelines recommending the use of LMWH for postpartum populations are based on expert opinion and extrapolate from other surgical fields. The efficacy of LMWH to prevent VTE in obstetrics remains unproven and introduces risk of harm in the form of bleeding and wound complications. While use of LMWH postoperatively is standard of care for most surgical fields, we are uncertain if the same benefits are present for obstetric patients who are generally younger, healthier, and potentially more mobile post-operatively. Experts are split with some calling for more rapid and widespread uptake of prophylaxis in the U.S. while others recommend against widespread uptake of LMWH prophylaxis. The result has been highly variable practice in the U.S. with rates of pharmacologic prophylaxis ranging from 1 to 85%. It is **imperative** that prospective research be performed to understand the efficacy of LMWH prophylaxis for reduction of VTE in postpartum individuals.

Before a large-scale, multicenter, rigorous clinical trial addressing efficacy of postpartum LMWH to prevent VTE can be completed, we must first address **critical knowledge gaps** including the feasibility of such a trial and understanding patient perspectives and information needs on the risk-benefit tradeoffs of LMWH prophylaxis versus risk of VTE. A randomized controlled trial (RCT) of postpartum patients at the individual patient level will require thousands of patients to achieve statistical power to detect a difference in rates of VTE by receipt of LMWH prophylaxis versus placebo. There is an **urgent** need to determine whether patients are willing to be randomized to LMWH prophylaxis or placebo, complete the therapy and follow-up. A future trial should also consider patient-centered outcomes. For instance, one patient may only perceive benefit from LMWH prophylaxis if the underlying risk for VTE is greater than 3%, while another patient may favor the potential risks of LMWH prophylaxis even for a VTE risk as low as <1%. Understanding patients' priorities in care and how best to educate patients to enable them to make decisions surrounding VTE prophylaxis is instrumental for future work.

OBJECTIVE / STUDY AIMS

Aim 1. Evaluate the feasibility of randomizing patients to LMWH versus placebo following cesarean delivery. Working hypothesis: Among eligible individuals, at least 35% will enroll, undergo randomization, and complete their allocated treatment.

Aim 2. Determine information needs, values, and outcome priorities influencing postpartum VTE risk communication. Working hypothesis: The majority of patients will consider risks of LMWH prophylaxis acceptable if reduction in VTE can be achieved.

METHODS

Specific Aim 1. Evaluate the feasibility of randomizing patients to LMWH versus placebo following cesarean delivery.

Study Design. The proposed research design is a pilot trial of postpartum patients randomized to weight-based LMWH prophylaxis or placebo for VTE prevention. This pilot will test the feasibility of a future large, multicenter RCT.

Study Population and Setting. Individuals aged 18 years or older undergoing cesarean delivery at the University of Utah Health will be considered eligible. Exclusion criteria include: contraindication to anticoagulation, plan for therapeutic anticoagulation, renal dysfunction (creatinine clearance <30mL/minute), history of VTE, high risk thrombophilia, or receipt of antepartum anticoagulation (for >2 weeks). Eligible individuals will be approached prior to delivery or within 12 hours postpartum. Informed, written consent will be obtained.

Procedures & Data Collection. Individuals will be randomized to receive either (1) weight-based dosing of LMWH or (2) no therapy after cesarean delivery. Weight-based dosing of LMWH will be 0.5mg/kg rounded to the nearest 10mg every 12 hours based on admission weight. No therapy will be no pharmacologic prophylaxis. Individuals will be randomized in a 1:1 ratio utilizing a permuted block method of randomization with a block size of 6 using REDCap. Participants and clinicians will be unblinded to randomization arm. The intervention, LMWH, will be initiated at 12 hours post-delivery consistent with obstetric anesthesia guidelines. Individuals will receive therapy inpatient and for 14 days following hospital discharge.

The remainder of postpartum care will be per standard institutional practice. Deferral of a dose or discontinuation of therapy early is at the discretion of the clinical care team. All individuals will receive mechanical prophylaxis with sequential compression devices (SCDs) intraoperatively and postoperatively until ambulatory per institutional protocol.

Detailed medical record abstraction will be completed for demographics, medical and obstetric history, delivery outcomes, and postpartum course. Final follow-up and outcomes will be ascertained at 6 weeks postpartum.

[figure not shown]
Outcomes. The primary outcome is feasibility, as defined by ≥35% enrollment of eligible individuals and retention ≥85% of enrolled individuals through all study procedures.^{1,2}

Secondary feasibility outcomes will include number of eligible patients per month, enrollment rate (proportion of eligible patients enrolled), and dropout rate. Reasons for enrollment refusal and withdrawal from the study will be elicited and tracked. By design, this pilot trial will not address efficacy or safety outcomes between intervention arms. However, these additional secondary outcomes will be tracked: objectively diagnosed VTE, wound hematoma, or bleeding complication (including readmission or return to the operating room) within 6 weeks postpartum.

Sample Size. The sample size for this pilot was calculated considering available data at UUH with 4,500 deliveries annually with a cesarean delivery rate of 22%. This provides approximately 990 patients anticipated to be eligible over the course of 12 months for the proposed pilot RCT. The sample size also uses statistical power considerations for a future multicenter RCT comparing LMWH to no therapy. Using preliminary data from our institution, an asymptomatic postpartum deep vein thrombosis (DVT) rate is estimated at ~2%. Considering a range of assumptions, 5,195 participants per group for an individual patient RCT would be necessary to detect a 35% reduction in rates of asymptomatic DVT. Modeled across a range of available centers, this trial could be completed in 1-2 years depending on annual enrollment (Figure 1).

To test these assumptions at UUH, an institution anticipated to be enrolling in a future multicenter trial, we determined a sample size of 22 individuals per month enrolled and retained using parameters of 35%

Figure 1. Sample size considerations for future multicenter RCT

enrollment of eligible individuals and 85% retention through the study procedures would be feasible. We plan for a one-month ramp up and three months of enrollment to assess feasibility.

Statistical Analysis Plan. For all outcomes, the proportion meeting the outcome with 95% confidence interval will be reported. A descriptive summary of reasons for patient refusal to participate or withdrawal will also be reported.

Potential Problems & Alternative Strategies. Some individuals may not want to participate in an RCT of LMWH versus no therapy, or may have stated preferences for one study arm. These perspectives are valuable to inform future trial modifications and determine enrollment feasibility. There are approximately 4,500 deliveries annually at UUH with an institutional cesarean rate of approximately 22%. This will provide ample sample size to complete the feasibility pilot.

Safety Monitoring. There is equipoise for a comparative trial between LMWH prophylaxis and no therapy. However, safety concerns may arise during the course of this pilot trial. Adverse events (AEs) and serious adverse events (SAEs) will be submitted to the institutional review board (IRB) and monitored through a data safety monitoring board (DSMB).

Specific Aim 2. Determine information needs, values, and outcome priorities influencing postpartum VTE risk communication.

Study Design. We will complete semi-structured interviews of patients to collect data on patient information needs and values about VTE risk communication, preventative interventions such as LMWH, and patient priorities related to risks of VTE versus preventative interventions. Interviews of obstetric providers will explore barriers to counseling on VTE risk and interventions.

Study Population and Setting. Patients meeting inclusion/exclusion criteria for the pilot trial (see *Specific Aim 1*) will be eligible for participation. Recruitment will be inpatient after delivery or from the UUH outpatient obstetric clinics at the time of postpartum clinic visit. Obstetric providers, including physicians and advanced practice clinicians (e.g., nurse midwives, nurse practitioners), at UUH will be asked to participate via departmental meetings and e-mail.

Procedures & Data Collection. All interviews will be conducted, in-person or virtual, by trained personnel. Written informed consent will be obtained prior to interviews. Patients will be interviewed 6-12 weeks after delivery. Obstetric providers will be interviewed over the course of the grant period. These facilitated interviews will last 60 minutes. Interviews will assess perspectives on: (1) patient information needs on VTE risk; (2) values around interventions; (3) outcome priorities for decision-making around risks of VTE versus risks of preventative interventions such as LMWH. These will also assess barriers and facilitators to communication that may be incorporated into future decision-aids or clinical practice. Interviews will be audio recorded and transcribed.

Detailed medical record abstraction will be completed for demographics, medical and obstetric history, delivery outcomes, and postpartum course for included patients. Measured characteristics of obstetric providers will include self-reported age, race, ethnicity, gender identity, years in practice, provider type, and provider services.

Outcomes. The outcome of this aim will be qualitative data that will inform future development of patient and provider education tools to aid in decision-making around VTE prevention.

Sample Size. We anticipate completing 15 semi-structured patient interviews and 10 semi-structured obstetric provider interviews. This sample size was selected based on available literature informing anticipated thematic saturation.

Statistical Analysis Plan. The transcribed interviews will be imported into a qualitative analytics software program. Qualitative data analysis will be completed following a standardized coding framework to identify common themes, as previously used by [name] group.³⁻⁵ In brief, an initial coding template will be defined, each transcript will be coded to identify recurrent and new themes, and coding frequency will be summarized.

Potential Problems & Alternative Strategies. There may be inadequate patient recruitment for interviews. However, based on the estimated population sample available for enrollment (see *Specific Aim 1*), relatively small sample size needed, and UUH record of high recruitment and retention, we anticipate adequate sample size will be achieved. Patient incentivization with gift cards may be added if recruitment is lower than expected.

There are over 75 obstetric providers eligible for recruitment through UUH. Using direct solicitation, which has been found to be an effective method for clinician recruitment, we anticipate achieving the necessary provider sample size.

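### Does a single fixed block size of 6 in this open-label, one-site pilot make allocation too predictable?

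*Combined protocol and SAP*

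**What the plan says.** Specific Aim 1, Procedures & Data Collection, gives the allocation rule: "Individuals will be randomized in a 1:1 ratio utilizing a permuted block method of randomization with a block size of 6 using REDCap". It adds: "Participants and clinicians will be unblinded to randomization arm". Study Population and Setting names a single institution: "Individuals aged 18 years or older undergoing cesarean delivery at the University of Utah Health will be considered eligible". No stratification factor is named, so there is one allocation stream. On timing, the same section says: "Eligible individuals will be approached prior to delivery or within 12 hours postpartum". The documents do not say when randomization follows the approach, who sees the running list of allocations, or whether recruiting staff are told the block size.

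The primary outcome (Outcomes) is feasibility: at least 35% of eligible individuals enrolled and at least 85% of those enrolled retained. Both proportions are taken over the whole trial. On comparisons between arms, Outcomes says: "By design, this pilot trial will not address efficacy or safety outcomes between intervention arms". The Statistical Analysis Plan for this aim says: "For all outcomes, the proportion meeting the outcome with 95% confidence interval will be reported".

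**The concern.** With one fixed block size, every block must end in balance. Once three patients in a block have gone to one arm, the rest of that block is determined. Someone who knows the size and has watched the allocations can then name the next arm before approaching the next patient. The open-label design makes past allocations visible, the single site gives one sequence to follow, and the block size is printed in the protocol.

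There is also a plausible motive. Potential Problems & Alternative Strategies anticipates arm preferences: "Some individuals may not want to participate in an RCT of LMWH versus no therapy, or may have stated preferences for one study arm". The Background describes divided expert opinion and prophylaxis rates from 1 to 85%. In a trial that compares arms, foreknowledge of this kind lets recruiters steer patients and can bias the treatment effect. Random block sizes are a common, inexpensive safeguard, so their absence catches the eye.

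**Working it through.** The plan gives no predictability figure, so there is none to reproduce. The inputs are the 1:1 ratio and block size of 6 (Procedures & Data Collection), and the accrual figures in Sample Size: 22 per month enrolled and retained, 85% retention, three months of enrollment after the ramp-up.

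**Number randomized.** 22 / 0.85 × 3 = 77.6, about 78. This is 13 full blocks of 6.

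**Fixed block of 6.** There are C(6,3) = 20 equally likely sequences. The last allocation is always forced: 12 sequences have a forced tail of 1, 6 have a tail of 2, and 2 have a tail of 3.

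- Certain allocations per block: (12×1 + 6×2 + 2×3)/20 = 30/20 = 1.5. Share: 1.5/6 = 25.0%, or 13 × 1.5 = 19.5 of 78.
- Correct best guesses per block of 2m, with m = 3: m + 2^(2m−1)/C(2m,m) − 1/2 = 3 + 32/20 − 0.5 = 4.1. Share: 4.1/6 = 68.3%.
- With one patient randomized between prediction and allocation, each tail shortens by one: (6×1 + 2×2)/20 = 0.5 per block, or 8.3%. With two in between: (2×1)/20 = 0.1, or 1.7%. With three: 0%.

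**Blocks of 4, 6 and 8 in random order.** This was simulated at N = 78 with equally likely sizes. The observer knows the three possible sizes but not their order, sees all past allocations and updates by Bayes' rule. Shares of allocations predictable at each confidence level, with no lag:

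| Confidence in next arm | Fixed 6 | 4/6/8 mixed |
|---|---|---|
| certain | 25.0% | about 2.3% |
| at least 90% | 25.0% | about 5% |
| at least 85% | 25.0% | about 10% |
| at least 80% | 25.0% | about 24% |
| at least 75% | 31.7% | about 35% |
| best-guess accuracy | 68.3% | about 67.9% |

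The 31.7% follows directly. After two like allocations at the start of a block (probability 2 × 3/6 × 2/5 = 0.4 per block), the next arm has probability 3/4. That adds 0.4/6 = 6.7% to the 25.0%.

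The large contrast therefore exists only at or near certainty. At 80% confidence the two schemes differ by about one percentage point, and at 75% the mixed scheme is slightly more predictable. Many allocations that were certain become 80 to 90% predictable, which is enough for anyone inclined to steer.

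**Lag.** The interval between prediction and randomization is not documented. Assume 78 patients over 91 days (0.86 per day) and Poisson arrivals. Weighting the lag-specific figures gives these certain shares, fixed against mixed:

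- 12 hours (mean 0.43 patients in between): 0.651×25.0 + 0.279×8.3 + 0.060×1.7 = 18.7%, against 2.0%.
- 2 days: 7.5% against 1.1%.
- 3 days: 4.0% against 0.7%.
- 7 days: 0.3% against 0.1%.

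Longer lags are possible because approach before delivery is allowed.

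**Link to the planned results.** Steering by arm distorts the comparison between arms. The plan makes no such comparison: its decision quantities are two pooled proportions, and the Statistical Analysis Plan names no analysis by arm. Foreknowledge could reach a pooled proportion only if it changed how many patients enrolled or stayed. Nothing in the documents allows that effect to be sized.

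**The case for a change.** The best case for a change is that certainty differs in kind from a good guess. A recruiter who knows the next arm can delay an approach or tell a patient what is coming. Enrollment, a component of the primary outcome, arises at exactly that step. Arm preferences are anticipated, the block size is in the protocol, and the pilot rehearses a larger trial in which concealment will matter. Mixed blocks need only a new allocation table for patients not yet randomized. The balance cost is small: at 78 randomized, a mean final imbalance of 0.56 patients, against 0 with fixed 6.

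The arithmetic behind this stands. Near-certain foreknowledge under full information and no lag would fall from 25.0% to about 2.3%, and even a 12-hour lag leaves 18.7% against 2.0%. What does not follow is a consequence for this pilot. Being unblinded means that participants and clinicians know the arm a patient received; it does not establish that recruiters hold the ordered list. The 2.3% itself depends on concealing the order of sizes: if each block's size were learned, certainty would return to about 24 to 25%. The argument about the larger trial concerns that trial's protocol, where the choice can be made on its own merits.

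**Conclusion.** The concern does not hold. Permuted blocks of 6 are a valid and clearly stated method, and they contradict nothing else in the plan. The planned conclusions rest on pooled enrollment and retention, and no analysis that depends on comparable arms is named. Predictability of the next arm therefore has no direct route to any planned result. An indirect effect on pooled enrollment or retention cannot be excluded, but it cannot be quantified from the documents either.

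The 25% is an upper bound for an observer with full information and no lag. The alternative improves on it only near certainty: about 23 percentage points for certain allocations, about 1 point at 80% confidence, and under half a point in best-guess accuracy.

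This rests on three assumptions. About 78 patients are randomized. The mixed sizes are equally likely and their order is hidden. The open-label description in Procedures & Data Collection is the operative one, although the aims speak of placebo; masked allocation would only weaken the concern. If the pilot later added a comparison between arms, the question would need to be reopened.

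### Aim 1 hypothesises completion of allocated treatment, but no feasibility outcome measures it in either arm, so the pilot can pass without showing that the open-label arms held

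*Combined protocol and SAP*

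**What the plan says.** The Aim 1 working hypothesis (Objective / Study Aims) reads: "Among eligible individuals, at least 35% will enroll, undergo randomization, and complete their allocated treatment".

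The Outcomes paragraph of Specific Aim 1 sets a different test: "The primary outcome is feasibility, as defined by ≥35% enrollment of eligible individuals and retention ≥85% of enrolled individuals through all study procedures". It then adds: "Secondary feasibility outcomes will include number of eligible patients per month, enrollment rate (proportion of eligible patients enrolled), and dropout rate". On reasons, it says only this: "Reasons for enrollment refusal and withdrawal from the study will be elicited and tracked". The Statistical Analysis Plan reports a proportion with a 95% confidence interval for each of these outcomes and adds nothing on treatment received.

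Under Procedures & Data Collection, the comparator is defined by "No therapy will be no pharmacologic prophylaxis". Participants and clinicians know the arm. LMWH runs through the inpatient stay and for 14 days after discharge, and final follow-up is at 6 weeks. On care outside the allocation, and on departures from it, the section says: "The remainder of postpartum care will be per standard institutional practice. Deferral of a dose or discontinuation of therapy early is at the discretion of" treating clinicians.

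The Background notes that "national guidelines have called for institutional protocols to categorize risk in postpartum individuals and implement corresponding pharmacologic thromboprophylaxis", and that U.S. use of pharmacologic prophylaxis ranges from 1% to 85%. The exclusions begin with "contraindication to anticoagulation, plan for therapeutic anticoagulation, renal dysfunction" and go on to prior VTE, high-risk thrombophilia and antepartum anticoagulation for more than 2 weeks. They do not remove patients whose team might favour prophylaxis on other risk grounds.

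**The concern.** The pilot exists to show whether a large trial of LMWH is workable. In an open-label comparison with no therapy, one thing to learn is whether each arm gets what it was allocated. The hypothesis recognises this, but the outcomes do not carry it through.

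Two kinds of departure can go unrecorded in the feasibility result: a no-therapy participant who is given pharmacologic prophylaxis, and an LMWH participant who stops early. Neither has refused, withdrawn or dropped out. If both are followed to 6 weeks, both can count as enrolled and retained. The pilot could then report feasibility without saying how far the treatment contrast was preserved, and the multicenter trial would be planned without that figure.

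**Working it through.** **1. The hypothesis against the criterion.**

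| Element | Hypothesis | Primary outcome | Secondary feasibility outcomes |
|---|---|---|---|
| Enrollment | yes | yes, at least 35% of eligible | yes |
| Staying in the study | implied | yes, at least 85% of enrolled | dropout rate |
| Completing allocated treatment | yes | not named | not named |

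The thresholds also do not add up to the hypothesis. If both are just met, 0.35 × 0.85 = 29.75% of eligible individuals are enrolled and retained. That is below 35% even if everyone adheres. With 85% completing, enrollment would have to reach 0.35 / 0.85 = 41.2%. If 10% or 20% of those retained departed from allocation (assumed shares), 29.75% would become 26.8% or 23.8%.

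**2. What the criterion can miss in the pilot.** The plan's target is 22 enrolled and retained per month for three months: 22 × 3 = 66, or about 33 per arm at 1:1. If retention means follow-up to 6 weeks, all 33 no-therapy participants count as retained whether 0 or 33 of them received LMWH.

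**3. The plan's figure for the future trial.** Inputs from the Sample Size paragraph are a DVT rate of about 2% and a 35% reduction, so 2.0% against 0.02 × 0.65 = 1.3%. Alpha and power are not stated; I assume two-sided 5% and 80%. With unpooled variance:

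n = (1.960 + 0.842)² × (0.02 × 0.98 + 0.013 × 0.987) / 0.007² = 5,194.8, which rounds up to 5,195 per group, matching the plan.

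**4. Illustration of control crossover.** Let a share c of the no-therapy arm receive LMWH with its full effect. The control rate becomes 0.02 × (1 − 0.35c), and the LMWH arm stays at 1.3%. The documents give no c, so a range is shown.

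| c (assumed) | Control rate | Observed reduction | n per group | Increase | Power at 5,195 |
|---|---|---|---|---|---|
| 0% | 2.00% | 35.0% | 5,195 | – | 80% |
| 10% | 1.93% | 32.6% | 6,281 | 21% | 72% |
| 20% | 1.86% | 30.1% | 7,781 | 50% | 63% |
| 30% | 1.79% | 27.4% | 9,942 | 91% | 53% |

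Early stopping in the LMWH arm would also dilute the contrast. It is not modelled, because the documents give neither a stopping rate nor the effect of a partial course.

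**5. What 33 per arm could show.** Exact 95% intervals: 0 of 33 crossing over gives 0% to 10.6%; 3 of 33 gives 1.9% to 24.3%; 7 of 33 gives 9.0% to 38.9%. This is imprecise, but enough to separate an arm that largely held from one that did not.

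**The case against.** - **The criterion may already include adherence.** The no-therapy allocation is set out under Procedures & Data Collection, and the primary outcome requires retention through the study procedures. On that reading a treated control has not completed them. This stands in part. The phrase is undefined, so a reader might infer that the criterion definitely excludes adherence, and the documents do not establish that. They leave it open, and nothing requires adherence to be reported.
- **The discretion sentence.** A reader might take it to let clinicians start LMWH in the no-therapy arm. It speaks only of deferring or stopping therapy. LMWH in a control would be a departure from allocation; the gap is that no outcome counts it.
- **Likelihood.** A reader might infer that crossover will be common. The 1% to 85% range is national, no rate or prophylaxis policy is given for this site, the Background also reports experts who advise against widespread use, and Safety Monitoring asserts equipoise. The objection stands: the frequency is unknown.
- **Size.** Giving every crossover the full 35% benefit, whatever the timing or number of doses, puts the figures near an upper bound for each rate. The plan says 5,195 came from a range of assumptions, and the accompanying figure is not shown, so one cannot conclude that non-adherence was ignored. The aims also say placebo where the methods say no therapy, so it is unclear how far open-label crossover would carry over.
- **Counting treated controls as not retained.** This tempting remedy is asymmetric if early stoppers on LMWH stay retained, and it merges adherence with follow-up. The objection stands, and the fix below avoids it.
- **A small descriptive pilot.** It does not address efficacy by design. But whether the arms hold is a feasibility question, and the plan's own hypothesis asks it.

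**Conclusion.** The point holds as a gap between hypothesis and outcomes. The named feasibility outcomes cannot test whether 35% of eligible individuals complete allocated treatment, and both thresholds can be met at 29.75% enrolled and retained. If retention is read as follow-up to 6 weeks, they can be met at any level of departure in either arm.

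The consequence for the future trial is illustrative only: about 6,280, 7,780 or 9,940 per group, against 5,195, at control crossover of 10%, 20% or 30%. This rests on assumed crossover rates, two-sided 5%, 80% power and full benefit in every crossover. The documents do not show that crossover will be frequent or that the future trial is undersized. This is a worthwhile, low-cost improvement.

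**What to change.** 1. Define the 85% threshold as follow-up retention to 6 weeks, and leave its value unchanged.
2. Add receipt of allocated treatment as a named feasibility outcome in both arms, reported by arm with a 95% CI. In the no-therapy arm this is the proportion given no pharmacologic prophylaxis; in the LMWH arm, the proportion completing the allocated course. State in advance how deferred doses count and where information on doses after discharge comes from, since the plan does not say.
3. Record the reason for each departure, alongside the reasons for refusal and withdrawal already tracked.
4. Report the proportion of eligible individuals who enroll, are randomized and complete allocated treatment, with its 95% CI, against the 35% in the hypothesis. Read the feasibility conclusion together with these figures.

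Clinical decisions stay with the care team; only the counting changes. The cost is a few fields within the planned record abstraction, possibly a question on post-discharge doses at the 6-week follow-up, and a feasibility result that may look less favourable.

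### Treatment completion is part of the Aim 1 hypothesis, but the plan has no clear measure of it and does not specify recording whether, when, by whom or why LMWH was deferred or stopped

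*Combined protocol and SAP*

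**What the plan says.** **The question posed.** The Background states a need to learn "whether patients are willing to be randomized to LMWH prophylaxis or placebo, complete the therapy and follow-up". (Its comparator wording differs from the no-therapy arm under Procedures; that is a separate matter.) The working hypothesis under Objective / Study Aims is that, among eligible individuals, "at least 35% will enroll, undergo randomization, and complete their allocated treatment".

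**The treatment.** Aim 1, Procedures & Data Collection: "Individuals will receive therapy inpatient and for 14 days following hospital discharge". The same section adds: "Deferral of a dose or discontinuation of therapy early is at the discretion of the clinical care team". It does not require the event, its initiator or its reason to be recorded.

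**The outcomes.** The primary outcome in Aim 1 is at least 35% enrollment of eligible individuals and "retention ≥85% of enrolled individuals through all study procedures". The secondary feasibility outcomes are "number of eligible patients per month, enrollment rate (proportion of eligible patients enrolled), and dropout rate".

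**The reasons.** Outcomes: "Reasons for enrollment refusal and withdrawal from the study will be elicited and tracked". Statistical Analysis Plan: "A descriptive summary of reasons for patient refusal to participate or withdrawal will also be reported".

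**Other data collected.** The chart is abstracted for the postpartum course, with final follow-up at 6 weeks. Wound hematoma and bleeding complications are tracked over the same 6 weeks. Adverse events go to the IRB and a DSMB.

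**The concern.** Leaving the study and stopping the study drug are different events. The plan collects reasons for the first only. A participant whose LMWH is stopped, whether by the care team or by her own choice, and who is still followed to 6 weeks has neither refused nor withdrawn.

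The plan does not say how such a participant is counted. If she counts as retained, the pilot could report high retention and low dropout while many participants did not complete LMWH. If she counts as not retained, a willing participant stopped on a clinician's order falls into the same figure as one who gave up.

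The distinction matters for the future trial because the remedies differ: support for participants in one case, agreement with clinicians in the other. Much of the treatment period lies in the 14 days after discharge. A decision made at home may never reach the chart, and analysts cannot recover it later if nobody asked.

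**Working it through.** **1. Each event set against the plan**

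| Event | Counted in a listed outcome? | Reason tracked and reported? |
|---|---|---|
| Refuses enrollment | Yes, enrollment rate | Yes |
| Withdraws from the study | Yes, dropout rate and retention | Yes |
| LMWH stopped early, follow-up completed | Unclear: depends on whether taking LMWH is a study procedure | Not specified |
| Dose deferred, follow-up completed | Unclear, same question | Not specified |

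The last two rows are the events that the discretion rule allows.

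**2. Size of the pilot**

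Inputs from Aim 1, Sample Size: 4,500 deliveries a year, 22% cesarean, 35% enrollment, 85% retention, 22 per month enrolled and retained, three months of enrollment. Allocation is 1:1 (Procedures).

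The plan's own monthly figure first: 4,500 × 0.22 = 990 a year; 990 / 12 = 82.5 a month; 82.5 × 0.35 = 28.9 enrolled; 28.9 × 0.85 = 24.5 retained. The plan states 22. The inputs and the stated figure do not quite agree, so both are carried forward.

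- From the stated 22: 22 × 3 = 66 retained; 66 / 0.85 = 77.6, so about 78 enrolled and 39 on LMWH.
- From the stated inputs: 82.5 × 0.35 × 3 = 86.6, so about 87 enrolled and 43 on LMWH.

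**3. How many stops decide the 85% criterion**

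Assume nobody is lost for any other reason, and vary only how a stop is counted.

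- 78 enrolled: 0.85 × 78 = 66.3, so 67 must be retained. Eleven losses pass and 12 fail. 12 / 39 = 31% of the LMWH arm.
- 87 enrolled: 0.85 × 87 = 73.95, so 74 must be retained. Thirteen losses pass and 14 fail. 14 / 43.5 = 32% of the arm.

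| Enrolled | Stops on LMWH | Retention if stops are losses | Retention if they are not | Dropout if they are not |
|---|---|---|---|---|
| 78 | 12 | 66/78 = 84.6%, fails | 100%, passes | 0% |
| 87 | 14 | 73/87 = 83.9%, fails | 100%, passes | 0% |

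The same data give opposite verdicts, and neither verdict says why LMWH ended.

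**4. The primary criteria against the hypothesis**

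Even if retention is read as treatment completion, meeting both criteria exactly gives 0.35 × 0.85 = 29.75% of eligible individuals enrolled and completing. The hypothesis says 35%, which at 85% completion needs enrollment of 0.35 / 0.85 = 41.2%. The hypothesized proportion therefore has to be reported directly.

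**5. Precision of an added proportion**

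Exact 95% intervals for stopping early: 4 of 39 (10%), 3% to 24%; 4 of 43 (9%), 3% to 22%; 13 of 43 (30%), 17% to 46%. These counts are illustrative.

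**The case against.** The best defense is that the plan already collects much of what is needed. Abstraction of the postpartum course could capture inpatient deferrals ordered by the care team. Wound hematoma and bleeding are tracked outcomes, and adverse events are reviewed by a DSMB. A reader might infer that the pilot cannot show anything about why therapy ended, or that it would lose its earliest safety signal. The documents support neither inference. Bleeding is captured whether or not a stop is recorded, and the Outcomes section says that the pilot is not designed to address safety between arms.

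A reader might also infer that a stop enters no listed outcome at all. That is not settled: if taking LMWH is a study procedure, a stop does enter retention. Nor should 31 to 32% be read as an expected stop rate. It is a constructed threshold that assumes no other losses.

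Finally, splitting about 39 to 43 people by initiator gives imprecise proportions, so a listing serves nearly as well. That is accepted and shapes the fix.

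What remains is that none of these sources is planned to be linked to a stop, its initiator or its reason. Chart abstraction would probably miss a participant's own decision at home.

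**Conclusion.** The concern holds in limited form. The plan makes completing allocated treatment part of its hypothesis and allows discretionary deferral and stopping. It does not clearly measure completion or specify recording whether, when, by whom or why LMWH was deferred or stopped. Participant choice, clinician order and bleeding therefore cannot be reliably separated, although some inpatient or bleeding-related stops may be identifiable.

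The effect could reach the primary outcome: 12 of 39 or 14 of about 43 stops would reverse the retention result, depending on an unstated counting rule. This rests on the enrollment range above, on no other losses, and on a stop rate that the documents do not give. The trial's validity is not in question. What is at stake is whether its question about completing therapy gets an interpretable answer. The change is worth making before enrollment, because reasons not asked for prospectively are hard to recover.

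**What to change.** Leave the clinical rule for deferral and discontinuation unchanged.

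1. **Record.** Extend the tracking sentence in Aim 1, Outcomes, so that every deferral and early discontinuation of LMWH is recorded with its date, initiator (participant or care team) and reason (bleeding or wound event, other medical, participant preference, other). Take this from the chart for the inpatient stay. For the 14 days after discharge, ask the participant at the planned 6-week follow-up.
2. **Measure.** Add a secondary feasibility outcome: the proportion completing allocated treatment, with 95% CI. Define completion for each arm, and state whether an early stop counts against retention. Report it separately from study withdrawal and loss to follow-up.
3. **Match the hypothesis.** Report the proportion of eligible individuals who enroll and complete allocated treatment, with 95% CI.
4. **Describe.** In the Statistical Analysis Plan, extend the summary of reasons to a descriptive listing of stops by initiator and reason.

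The cost is one short REDCap form, one added question at the 6-week contact and two proportions. The sample size does not change. Answers at 6 weeks about the first weeks after discharge are subject to recall error, and intervals will be wide with about 39 to 43 participants on LMWH.
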